additional preoperative educational materials or resources other than what is currently provided by their care team. This usually includes a routine phone call, text, or email from a pre-operative staff member within a few days of the child's scheduled procedure to provide basic information about fasting, when to arrive at the hospital, and anything additional that needs to be done prior to the procedure (e.g. COVID-19 testing), when applicable. Any specific information about the anesthetic will be deferred to the anesthesia team for the surgical day, per usual.

In both the intervention and control groups, if parents specifically request additional information to prepare for surgery, pre-op staff may send them the "Social Story" developed by the Autism Spectrum Center, Child Life Services, and Waltham Surgical Services. This document provides an age-appropriate step-by-step guide as to what to do and what to expect on the day of surgery.

On the day of surgery, all parents participating in the study, regardless of group assignment, will receive surveys to complete in the pre-operative holding area via REDCap®. The surveys will be given to the parent who consented to the study. If both parents are present, and both consented to the study, they will both receive surveys to complete. A research staff member trained for reliability and blinded to the study arm will assess the child for signs of anxiety in the pre-op holding area.

For both groups, once the surgical procedure is complete, and the child has gone to the PACU, Emergence Agitation/Delirium will be assessed per standard of care at Waltham by the bedside PACU nurse using the Pediatric Agitation Emergence Delirium Scale (PAED). The

research team will collect this PAED information retrospectively from the child's electronic medical record.

(4) Definition of Primary and Secondary Outcomes/Endpoints:

See Table 1 for Summary of Outcomes/Measures

Patient Demographics

Parental age, gender, ethnicity, and highest education level achieved will be collected as part of the REDCap® preoperative survey to better understand the pilot group and educational needs (Appendix B).

Primary Outcomes

Parental Utilization:

- *When provided with the opportunity to obtain more information as it relates to the perioperative experience, do parents and their children use the tool?*
- *How many times did they access the tool and for how long?*
- *Were there any barriers to accessing the PIRA tool?*

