If there were problems surrounding the accessibility, content, language, or any other system issues, this will affect utilization and the PIRAs future potential impact.

Regardless of the medium, materials, or content provided, no preoperative educational program can be successful and sustainable unless readily adopted and utilized by parents and children. As such, a primary outcome will evaluate whether families actually viewed the materials, with whom, and how much time they spent with the PIRA.

Parental Perceived Impact and Impressions:

- *Did parents find the tool subjectively helpful?*
- *What improvements or changes in content or language would they consider?*
- *Would parents recommend the PIRA to future families?*

Identifying parental perceived benefits or drawbacks to the PIRA may elucidate the familial interactions and how they feel about their educational experience in a different way than anxiety or other objective data. Similarly, given the novel nature of the PIRA, it is important to identify any educational gaps and potential for future topics and educational needs. If parents believe the PIRA improved their preoperative experience, it could be useful for future families.

Secondary Outcomes

Child Anxiety in Preoperative Waiting:

As discussed, more than 60% of pediatric patients have been found to suffer from anxiety in the preoperative period. The effects of anxiety may have behavioral sequelae, or Postoperative Maladaptive Behaviors (POMB), which can last up to a year or longer. Therefore, reducing anxiety levels should be a priority of any educational tool for pediatrics. Numerous randomized control trials have demonstrated decreased child anxiety in preoperative waiting for those patients who participated in preoperative educational programs including videos, tours, apps, games, and books. *Is there a similar difference in the control and intervention groups' preoperative anxiety with this PIRA intervention?*

Parental Anxiety in Preoperative Waiting:

In several cited studies, parental anxiety directly correlates with the pediatric patient's anxiety. Thus limiting or reducing parental anxiety is an important part of a preoperative education intervention. *Does improved communication and education decrease parental anxiety?* An intervention which serves to improve communication between the parent/child as well as the parent/anesthesia provider AND reduce parental anxiety would perhaps provide significant benefits.

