Emergence from Anesthesia: Presence or absence of emergence agitation/delirium (ED):

Depending on the study, ED has an incidence between 10-80%, with most studies showing 30-50% of children having ED after a general anesthetic (Przybylo et al., 2003; Ringblom et al., 2018). ED can be extremely distressing for parents, delay discharge from post-anesthesia care unit (PACU), can result in injury to the patient or staff (due to uncontrolled flailing, kicking, punching), and can also potentially result in the unintentional dislodgement of intravenous catheters or other tubes (e.g. nasogastric, gastrostomy, chest, endotracheal tubes). Data have shown a reduction in ED incidence with the use of preoperative education programs (Kain et al., 2004). *Is there any effect on the incidence of ED for children who have more interactive preoperative education, such as PIRA, compared to standard information?*

(5) Data Collection Methods, Assessments, Interventions and Schedule

On the day of the surgical procedure, participating parents in both the PIRA and the control groups will receive the same in-person surveys in the preoperative holding area. Surveys will be administered via REDCap® and completed on iPads which have been given to the

parents by a member of the research team (Appendix B). In both groups, the parent(s) who consented to the study and there on the day of surgery will be given the surveys.

The surveys will have no identifying questions and will be automatically uploaded to REDCap®. They will be accessible only to members of the research team. Children will not be asked to complete any surveys but will be observed in the pre-op holding area by a member of the research team and in the PACU by a PACU nurse, as per standard of care at BCH Waltham. Both will have been trained for reliability in conducting the study-specific assessment tools.

Pediatric Anesthesia Emergence Delirium (PAED) scores will be collected retrospectively from the child's electronic medical record. All data collected will be de-identified and presented or published in aggregate. The research team will provide a finished copy of the manuscript upon request.

Primary Outcomes Data

Parental Utilization:

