Appendix A. Email Instructions for use of the Interactive Anesthesia Education Program

To the Parent/Guardian of _____:

Thank you for your participation in this study. Please refer to the below instructions for using the PIRA program.

Access to the education program is by a computer or tablet device through the hyperlink included below on the Google Chrome browser ONLY. Please note, a mobile device and other internet browsers will not work with this online tool.

Along with the hyperlink, we have also provided you with a unique username and password. Once you click on the hyperlink, you will be prompted to enter this information to access the program.

Link:

Username:

Password:

When you are ready to review the education materials, click, “start at the beginning” You or your child will be required to periodically answer questions or respond by clicking the mouse to move it forward. Either you or your child can click, but please make sure that both you and your child are able to see and hear the teaching the entire time.

If you need to stop for a prolonged period of time for whatever reason, you can start at the beginning again to ensure no content is missed. Refreshing the page will reset the program. It will not save where you left off.

You will receive one email reminder a few days prior to your child’s surgical date reminding you to complete the PIRA at least once with your child. If you have any problems accessing the education program, or any issues during its use, please contact the study PI, [name], at [contact] or [contact].

Thank you,

[name]

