Appendix B. Parental PIRA Survey

Please complete the survey, below. Your responses to the following questions will better help us to understand how to improve our preoperative education and communication for parents and their children. As a study participant, you were randomly assigned to either receive an online interactive tool focused on educating children, named PIRA, or you received our standard preoperative information. If any of the below questions make you uncomfortable, please leave them blank.

Demographics:

Q1. Your current age (in years):

Q2. Gender:

Q3. Ethnicity:

Q4. Highest level of education achieved:

Pre-Operative Education Experience:

Q1. What of the following statements describes your experience with the anesthesia education agent, Ira? (Select all that apply)

- I did not receive the link to Ira
- I received the link to Ira, but did not watch it
- I received the link to Ira, but a different care provider or family member watched Ira.
- I watched Ira WITHOUT my child
- I watched Ira WITH my child
- I had a hard time using Ira
- My child liked using or watching Ira
- My child seemed LESS stressed about surgery or anesthesia because they watched Ira
- My child seemed MORE stressed about surgery or anesthesia because they watched Ira
- I understood anesthesia better after watching Ira
- Ira helped me talk to my child about anesthesia and surgery
- Ira helped answer questions about anesthesia
- I felt less stressed about surgery or anesthesia because I watched Ira
- Ira made my surgery experience BETTER
- Ira made my surgery experience WORSE

- Ira was difficult to use or understand

Q2. In total, about how long did you spend with the interactive education agent, Ira?

- Less than 5 minutes
- 5-30 minutes
- 30-60 minutes
- More than 60 minutes
- I did not view the agent

Q3. How likely are you to recommend the interactive education agent, Ira, to future families? (Skip if you did not receive or view Ira)

This is a sliding scale

0 = Not at all Likely to Recommend-----100 = Extremely likely to recommend

Q4. Write any topics that were missing, unclear, or absent from the interactive education agent, Ira. (Skip if you did not receive or view Ira)

**Free Text Response_____

Q5. Write any suggestions for future improvements to the interactive education agent, Ira. This may include any difficulties in accessing or using it. (Skip if you did not receive Ira)

**Free Text Response_____

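### The parent survey has no direct item on whether the child saw the PIRA without the responding parent, and its time question covers only the respondent

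*Combined protocol and SAP*

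**What the plan says.** Aim 1 (Section A) is access and utilization by parent and child. Section D(4) poses the question as "do parents and their children use the tool" and states that "a primary outcome will evaluate whether families actually viewed the materials, with whom, and how much time they spent with the PIRA". The outcome therefore has three parts, stated for families: viewed or not, with whom, and for how long.

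Two sources are described in Section D(5). The program logs time, accesses and timestamped clicks, and the parent survey adds self-report. Table 1 lists only the parent survey for utilization. Section D(5) also says that "the parent(s) who consented to the study and there on the day of surgery will be given the surveys".

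In Appendix B, Q1 is a multiple-response item: "What of the following statements describes your experience with the anesthesia education agent, Ira? (Select all that apply". The relevant options are:
- "I watched Ira WITH my child", and its counterpart for watching without the child. Both have the respondent as viewer.
- "I received the link to Ira, but a different care provider or family member watched Ira". This does not mention the child.
- Three options on the child's reaction: the child liked it, or seemed less or more stressed because of it.

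Q2 asks "In total, about how long did you spend with the interactive education agent, Ira" and offers one zero category, for a respondent who did not view the agent. Section D(3) describes log-in details issued to families, and Appendix A says "Either you or your child can click".

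**The concern.** The survey is the only planned source that could say with whom the PIRA was watched, and that is a stated part of a primary outcome. It answers directly only when the responding parent was a viewer. The form anticipates use by someone else, since it has an option for it, but then leaves out the fact that the outcome asks for.

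In a feasibility pilot, utilization is a main product. The PIRA addresses the child by name, and the child's exposure is a natural route to any effect on the mYPAS or PAED. If the child's viewing is unknown for some families, the trial cannot fully answer its own question about use by children. The missing fact cannot be recovered from the log afterwards.

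**Working it through.** The plan states no figure on this point, so the check sets the outcome's three parts against the survey and the log for each way a family might use the tool.

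| Who used the PIRA | Q1: use recorded? | Q1: child's presence? | Q2: time | Program log |
|---|---|---|---|---|
| Respondent with child | Yes | Yes | Respondent's time | Family time and accesses |
| Respondent without child | Yes | Yes (absent) | Respondent's time | Family time and accesses |
| Another caregiver with child | Yes, by another person | No direct item | Non-viewer answer | Family time and accesses; viewer unknown |
| Another caregiver without child | Yes, by another person | No direct item | Non-viewer answer | Family time and accesses; viewer unknown |
| Child alone | No option written for it | No direct item | Non-viewer answer | Family time and accesses; viewer unknown |
| Nobody | Yes, as not watched | Not applicable | Non-viewer answer | No use |

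**Reading the table**

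1. *Viewed or not.* Use by another caregiver is recorded in Q1, by an option separate from the one for a parent who had the link and did not watch. The log also shows whether the account was used.
2. *With whom.* The two rows for another caregiver can produce identical survey and log records. A ticked reaction option shows that the child was exposed. With all of them blank, a child who watched without a marked reaction looks the same as one who never watched. A respondent who was not there may also not know how the child reacted.
3. *Time.* Q2 gives the same answer in the last four rows. In three of them the log still holds the family's time, but it cannot divide that time between adult and child.

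**Size per family**

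Inputs from Section I: 38 recruited per group, 30 per group for analysis.

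- 1/38 = 0.026, or 2.6 percentage points of the PIRA group with child exposure unknown.
- 1/30 = 0.033, or 3.3 points.

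The documents give no rate of use by someone other than the respondent. As an assumption only, 5% to 20% of 38 families is 0.05 × 38 = 1.9 to 0.20 × 38 = 7.6, so about 2 to 8 families. If no reaction option was ticked in any of them, child utilization would be known only to within 2/38 = 5.3 to 8/38 = 21.1 points. That is the width of an unknown range, not a bias in one direction.

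**The case against.** The strongest reply is that the data are better than Q2 alone suggests. Q1 separates use by someone else from non-use. Its reaction options do not require the respondent to have watched and can be ticked together with the other-caregiver option. The log captures time and accesses whoever sat at the screen. If the viewer was a second parent who consented and is present, Section D(3) gives that parent a survey too. Appendix A asks that parent and child both follow the teaching throughout. The planned mYPAS comparison is a t-test between groups and does not use survey-reported exposure.

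All of this stands, and it rules out three stronger readings that a reader might infer:
- *That the survey cannot tell whether the child was exposed.* A ticked reaction option shows that the child was.
- *That such families are recorded as non-users with no time.* Only the respondent's Q2 answer reads that way. Q1 records the use, and the log holds the time.
- *That child use is understated by some 5 to 21 points.* This needs an assumed rate, exposure of the child in every such family, no reaction option ticked, and a rule that codes unknown as non-use. The documents contain no such rule.

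The reply does not close the question of with whom. The log is per family and either person may click. The reaction options inform only when ticked, and using them as a proxy would make measured exposure depend on how the child responded. Caregivers who did not consent, such as a grandparent or sitter, are not surveyed. An instruction to watch together does not record whether it was followed.

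**Conclusion.** The point holds as a gap in the questionnaire. Appendix B has no direct item on the child's viewing with someone other than the respondent, or alone, and Q2 measures the respondent's time rather than the child's or the family's. Family time and accesses are covered by the log, but Table 1 does not name it and the plan does not say how the two sources are combined.

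The overall size cannot be computed from the documents. Each affected family adds 2.6 points (of 38) or 3.3 points (of 30) of unknown child exposure. This assumes that no reaction option was ticked and that no second consenting parent who watched completed a survey. The planned between-group test is unaffected. This is a cheap improvement, worth making because the information is lost once the form has been used.

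**What to change.** In Appendix B, Q1:
- Split the option on a different care provider or family member into two: watched WITH my child, and watched WITHOUT my child.
- Add an option: My child watched Ira alone.

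In Appendix B, Q2: ask for the child's total time (with the respondent, with another caregiver, or alone) alongside the parent's own time.

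In Table 1: define child utilization as any Q1 option in which the child watched, and name the program log as the source for family time and number of accesses, with the survey as the source for who watched.

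The cost is a few REDCap options, one added time line and a short Table 1 edit. The form becomes slightly longer, and the child's time will be partly second-hand when the respondent was not present.

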The amount of time spent using the PIRA and the number of times the PIRA was accessed will be able to be collected via the program itself, stored on a secure Northeastern University Server, and will be accessible only to the study team. Each click of the mouse a user makes in the system will be timestamped and saved on the database. This information will be de-identified. Additionally, the parental survey administered by the research team member in the preoperative holding area will obtain self-reported data on PIRA access and time spent using the tool (Appendix B).

Parental perceived impact and impressions:

This outcome will be assessed in the same survey (Appendix B) as Parental Utilization. The survey will have no identifying questions and will be automatically uploaded to REDCap®, accessible only to members of the research team. Any data will be de-identified and presented in aggregate.

Secondary Outcomes Data

Child Anxiety in Preoperative Waiting:

Child anxiety will be assessed using the modified Yale Preoperative Anxiety Scale (mYPAS), an observational state anxiety measure for children containing 27 items in five categories (activity, emotional expressivity, state of arousal, vocalization, and use of parents). See Figure 1. The mYPAS has been validated for measuring childrens' anxiety (Kain et al., 1995; Kain et al., 1997). Members of the research team who will administer the mYPAS for this study will be trained for reliability. mYPAS scores range from 22.5 to 100, with higher scores indicating more anxiety.

Parental Anxiety in Preoperative Waiting:

Parental anxiety will be assessed using the State-Trait Anxiety Inventory (STAI). See Figure 2. This self-report anxiety instrument contains two separate 20-item subscales that measure trait (baseline) and state (situational) anxiety (Spielberger, 1973; Spielberger, 1983; Spielberger, 1989) This survey will take place in the preoperative holding area and will be administered in conjunction with the previous utilization/recommendation survey (Appendix B). The STAI is scored from 20-80, with higher scores indicating more anxiety.

Emergence from Anesthesia: Presence or absence of emergence agitation/delirium

(ED):

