Potential Gaps or Recommendations for Future Iterations (Primary)	Parental Survey, free text entry	See Appendix B Summarized for themes	Preoperative Waiting, self-reported.
Parental Anxiety (Secondary)	STAI	See Appendix B and Figure 2. Range 20-80, higher = greater anxiety	Preoperative Waiting, self-reported
Child Anxiety (Secondary)	mYPAS (Observational)	See Figure 1. Range 22.5-100	Preoperative Waiting, observed by a Research Assistant (RA)
Emergence from Anesthesia (ED) (Secondary)	PAED Scale (Observational)	See Figure 3. Range 0-20; Threshold for ED ≥ 12	PACU, observed by a Registered Nurse (RN) as per BCH standard of care.

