Q6. Self-evaluation questionnaire. Rate the following statements how they apply to you from 1 = Not at all to 4 = Very Much So

	1 = Not at all	2 = So me wh at	3 = Mo der y at	4 = Ver atel ch so
I feel calm				
I feel secure				
I am tense				
I feel strained				

I feel at
ease

I feel
upset

I am
presently
worrying
over
possible
misfortu
nes

I feel
satisfied

I feel
frightene
d

I feel
comforta
ble

I feel
self-
confiden
t

I feel
nervous

I am
jittery

I feel
indecisiv
e

I am
relaxed

I feel
content

I am
worried

I feel
confused

I feel steady	
I feel pleasant	

Figure 1. Modified Yale Preoperative Anxiety Scale (mYPAS) for Child Anxiety

Domain: Activity

1. Looking around, curious, playing with toys, reading (or other age-appropriate behavior); moves around holding area/treatment room to get toys or go to parent; may move toward OR equipment
2. Not exploring or playing, may look down, may fidget with hands or suck thumb (blanket); may sit close to parent while waiting, or play has a definite manic quality
3. Moving from toy to parent in unfocused manner, non-activity-derived movements, frenetic/frenzied movement or play; squirming, moving on table, may push mask away
4. Actively trying to get away, pushes with feet and arms, may move whole body; in waiting room, running around unfocused, not looking at toys or will not separate from parent

Domain: Vocalizations

1. Reading (nonvocalizing appropriate to activity), asking questions, making comments, babbling, laughing, readily answers questions but may be generally quiet; child too young to talk in social situations or too engrossed in play to respond
2. Responding to adults but whispers, "baby talk," only head nodding
3. Quiet, no sounds or responses to adults
4. Whimpering, moaning, groaning, silently crying
5. Crying or may be screaming "no"
6. Crying, screaming loudly, sustained (audible through mask)

Domain: Emotional Expressivity

1. Manifestly happy, smiling, or concentrating on play
2. Neutral, no visible expression on face
3. Worried (sad) to frightened, sad, worried, or tearful eyes
4. Distressed, crying, extremely upset, may have wide eyes

Domain: State of Apparent Arousal

1. Alert, looks around occasionally, notices/watches anesthesiologist (could be relaxed)
2. Withdrawn child sitting still and quiet, may be sucking on thumb or face turned in to adult
3. Vigilant looking quickly all around, may startle to sounds, eyes wide, body tense

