4. Panicked whimpering, may be crying or pushing others away, turns away

Figure 2. Parental State-Trait Anxiety Inventory (STAI) for Parental Anxiety

Self-evaluation questionnaire	STAI Form Y-1			
	1	2	3	4
1. I feel calm				
2. I feel secure				
3. I am tense				
4. I feel strained				
5. I feel at ease				
6. I feel upset				
7. I am presently worrying over possible misfortunes				
8. I feel satisfied				
9. I feel frightened				
10. I feel comfortable				
11. I feel self-confident				
12. I feel nervous				
13. I am jittery				
14. I feel indecisive				
15. I am relaxed				
16. I feel content				
17. I am worried				
18. I feel confused				
19. I feel steady				

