20. I feel pleasant				

1: Not at all, 2: Somewhat, 3: Moderately so, 4: Very much so

Figure 3. PACU Pediatric Anesthesia Emergence Delirium (PAED) for Anesthesia**Emergence Delirium**

Behavior	Not at all	Just a little	Quite a bit	Very much	Extremely
The child makes eye contact with the caregiver	4	3	2	1	0
The child's actions are purposeful	4	3	2	1	0
The child is aware of his/her surroundings	4	3	2	1	0
The child is restless	0	1	2	3	4
The child is inconsolable	0	1	2	3	4

K. References

- Akdağ, M. (2014). A multi-centric prospective study: Anxiety and associated factors among parents of children undergoing mild surgery in ENT. *Journal of Clinical and Experimental Investigations*, 5(2), 206–210.
- Aytekin, A., Doru, Ö., & Kucukoglu, S. (2016). The effects of distraction on preoperative anxiety level in children. *Journal of Perianesthesia Nursing: Official Journal of the American Society of Peranesthesia Nurses / American Society of Peranesthesia Nurses*, 31(1), 56–62.
- Bartik, K., & Toruner, E.K. (2017). Effectiveness of a preoperative preparation program on children's emotional states and parental anxiety. *Journal of Perianesthesia Nursing: Official Journal of the American Society of PeriAnesthesia Nurses / American Society of PeriAnesthesia Nurses*. <https://doi.org/10.1016/j.jopan.2017.09.008>
- Beringer, R. M., Greenwood, R., & Kilpatrick, N. (2013). Development and validation of the Pediatric anesthesia behavior score - an objective measure of behavior during induction of anesthesia. *Pediatric Anesthesia*, 24(2), 196–200.

- Buckley, A., & Savage, E. (2010). Preoperative information needs of children undergoing tonsillectomy. *Journal of Clinical Nursing*, 19(19-20), 2879–2887.

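### Parental STAI: D(5) describes trait and state subscales, but only one 20-item set is collected, and its instruction does not say whether to answer for the present moment or in general

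*Combined protocol and SAP*

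**What the plan says.** Section A (Aim 3) names parental preoperative anxiety as a between-group comparison, and D(4) and Table 1 list it as a secondary outcome. D(5) says it is assessed with the STAI, which "contains two separate 20-item subscales that measure trait (baseline) and state (situational) anxiety". The same paragraph says "This survey will take place in the preoperative holding area" and "The STAI is scored from 20-80, with higher scores indicating more anxiety". Table 1 gives one entry, labelled only STAI, with "Range 20-80, higher = greater anxiety", timed at preoperative waiting.

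The items appear in two places. Appendix B Q6 opens with "Rate the following statements how they apply to you from 1 = Not at all to 4 = Very Much So" and lists 20 statements. Figure 2, headed Form Y-1, lists the same statements, ends at "20. I feel pleasant" and carries the legend "1: Not at all, 2: Somewhat, 3: Moderately so, 4: Very much so". No second set of items appears in the document.

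Section H names a t-test for the mYPAS only. Quantitative data from the parental survey are to be summarised descriptively, with no mention of a trait score.

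**The concern.** There are two linked problems.

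First, a reader of D(5) would expect two scores, one for disposition and one for the situation. Only one can be calculated, and neither D(5) nor Table 1 says which subscale it is.

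Second, the protocol draws the distinction between baseline and situational anxiety, but the instruction put to parents does not. Asking how statements apply to the respondent allows two answers: how I feel now, or how I usually am. Several items, such as those on feeling secure, satisfied or self-confident, can be read either way. Q6 also follows five questions about experience with the agent, so nothing just before it directs the parent to the present moment.

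What is at stake is how clearly an Aim 3 outcome is measured. An education tool used in the days before surgery might change how a parent feels in the holding area, but is less likely to change general disposition. Answers of the second kind would be expected to weaken any contrast between the arms. Answers given under an ambiguous lead-in cannot be sorted out afterwards.

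**Working it through.** **1. Does the stated range fit one subscale or two?** The inputs are 20 items (Appendix B Q6 and Figure 2), each scored 1 to 4 (Q6 lead-in and Figure 2 legend).
- One set: 20 × 1 = 20 to 20 × 4 = 80. This reproduces the range in D(5) and Table 1.
- Two sets, as D(5) describes: 40 items, giving two separate scores of 20-80 or a combined 40 × 1 = 40 to 40 × 4 = 160. The document gives neither.

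So 20 items are collected, the other 20 that D(5) describes are absent, and no trait score can be derived.

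**2. Which subscale is it?** The items are present-tense statements of feeling, and one reads "I am presently worrying over possible misfortunes". Taken with D(5)'s account of two subscales, this points to the state set. It is an inference, because the document does not label Form Y-1 as state.

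**3. What fixes the time frame?**
- Setting: holding area (D(5)) and preoperative waiting (Table 1). This points to the present.
- Item wording: present tense throughout, but only 1 of 20 items names the present explicitly.
- Response options: degrees of intensity, with no time reference.
- Instruction in Q6: no time reference.

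The score is therefore anchored in part, by context, but not by the instruction.

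**4. What would a trait measure add?** Assume 30 independent parents per arm (the Section I figure, which is for children), 80% power, two-sided 0.05, and a state-trait correlation r of 0.4 to 0.7. The document gives no r.
- Unadjusted detectable difference, noncentral t: 0.736 SD. The normal approximation gives (1.960 + 0.842) × √(2/30) = 0.72 SD.
- Adjusted: 0.736 × √(1 − r²), ignoring the one degree of freedom used by the covariate.

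| r | √(1 − r²) | Detectable difference (SD) | Equivalent sample multiple, 1/(1 − r²) |
|---|---|---|---|
| 0.4 | 0.917 | 0.674 | 1.19 |
| 0.5 | 0.866 | 0.637 | 1.33 |
| 0.6 | 0.800 | 0.588 | 1.56 |
| 0.7 | 0.714 | 0.525 | 1.96 |

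**5. Is the sample size affected?** No. Section I bases it on the mYPAS (difference 6, SD 8). Power at 30 per group is 0.815 by the t-test, and 30/(1 − 0.2) = 37.5, rounded up to 38 per group, or 76 in total.

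**The case against.** The strongest reply is that this is a matter of wording. The D(5) sentence describes a published instrument and does not promise that both subscales will be scored. Everything operational (one range, one form, 20 items, one time point) points to a single situational score, and no aim or analysis uses a trait score. That stands. A reader might infer that the protocol promises a pre-intervention baseline and then fails to collect it. The text does not support this: the word baseline there explains the term trait and does not name a visit or a measurement.

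A reader might also infer that the score is not tied to the holding area at all. That goes too far, since D(5) and Table 1 fix the place and the items are in the present tense. What is missing is an explicit time frame in the instruction. An instruction line could have been lost from Figure 2 when the PDF was read, but the Q6 lead-in is legible and has none.

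The precision figures can fairly be challenged too. They rest on an assumed r, and they describe an adjusted comparison that Section H does not plan. D(3) gives surveys to both parents when both consented and are present, so the number of parents is not fixed at 30 per arm and parents of one child are not independent. The figures therefore show what an optional addition could gain. They do not measure a defect.

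The reply does not remove the ambiguity in Q6. That is the text parents answer, and changing it alters the measurement itself.

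**Conclusion.** The point holds in a limited form. D(5) describes two subscales, one is collected, and the outcome is not named as state anxiety. The Q6 instruction leaves parents free to answer in general terms, and the setting and tense guard against this only partly. The size of the effect on the comparison is unknown: nothing in the document shows how many parents would answer that way, so a claim that the PIRA effect is materially diluted cannot be made.

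Nor does the lack of a trait score bias the comparison. Randomisation keeps an unadjusted comparison of state scores valid, and chance imbalance in disposition is already allowed for in the test's error rate. What is forgone is precision and the ability to see such imbalance: a detectable difference of 0.74 SD instead of 0.67 to 0.53 SD, if r is 0.4 to 0.7 and there are 30 independent parents per arm.

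The Q6 change should be made. The relabelling is clarification that goes with it, and the trait form is optional.

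**What to change.** 1. Change the Q6 lead-in in Appendix B to ask how the parent feels right now, at this moment. Cost: one line in the REDCap survey. If any parents have already answered the present version, record which version each parent saw.
2. In D(5) and Table 1, name the outcome as parental state anxiety (Form Y-1, one score, 20-80), and say in D(5) that the trait subscale is not used unless item 3 is adopted. Cost: two wording edits.
3. Optional: collect the 20 trait items remotely at consent, before the random draw. Add to Section H a comparison of day-of-surgery state scores adjusted for trait, saying how two parents of one child are handled. Cost: a short extra form for each consenting parent, and a new remote step that must be finished before allocation, because the surveys are at present given only in person on the day of surgery.

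None of these changes affects the recruitment target of 76.
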